3.0 Inclusion and Exclusion Criteria

Potential subjects will be identified by electronic medical record searches, clinic schedules, inpatient lists, and word of mouth recommendation. A member of the study team will review the potential subject's medical records to confirm diagnosis, language, and care plan. If eligible, the caregiver and subject will be approached for participation. Eligibility will be confirmed with the caregiver verbally prior to obtaining informed consent.

Inclusion Criteria

- Presence of bone edema on STIR or T2 fat saturation sequence on MRI within 12 weeks of enrollment (optional)
- Whole body imaging evaluation (either WB MRI or bone scintigraphy) is optional
- Bone biopsy to exclude infection or malignancy when indicated

Exclusion Criteria

- History of or current malignancy
- Current infectious osteomyelitis
- Contraindication to the selected treatment agent

Adults who are unable to consent and lack a legal guardian, wards of the state, and prisoners will be excluded.

Caregivers will be reporting about the subject's medical history therefore they are not considered study subjects.

As this is a multicenter international study, sites will use local language such as Turkish, German, Italian, etc.

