8.0 Study Endpoints

Primary Endpoint: Determine the effectiveness of commonly used medications in SOP for patients with CNO.

Clinical, laboratory and imaging results as well as PROs will be collected at each clinical visit after enrollment. Enrolled subjects will be stratified based on their past disease course, past treatment. Response to medication will be calculated based on previously described by Beck et al.⁵ and Zhao et al.² at clinical visits prior to and after starting a new medication for comparison. Clinical disease activity score (CDAS) comprised of patient pain (0-10), patient global disease activity per report (0-10), clinical lesion count by physician, will be used to determine response. >=50% of reduction of CDAS is defined as favorable response.

Secondary Endpoint: Determine the risk factors for patients with NSAID-refractory CNO.

Patients will be classified as NSAID responders (significant improvement of pain, focal exam, ESR, CRP, imaging within 6 months of NSAIDs treatment), NSAID non-responders (requiring >6 weeks of systemic glucocorticoid, disease modifying anti rheumatic drugs, TNF inhibitors, bisphosphonate) based on treating physician's assessment. Baseline demographic, clinical, laboratory, imaging results will be compared between two groups and odds ratio will be calculated. There is no safety endpoint because it is an observational study that does not pose any risk to subjects.

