11.0 Data Analysis/Management

We will use multivariable linear mixed-effects regression models, with each treatment as the dependent variable and person as the random effect, to estimate the average treatment effect, as well as the mean difference between groups, and any interactions as relevant to the particular Aim. The model will adjust for age, gender, lesion number and past medication use. The FDR will be used separately in each Aim to account for multiple pair comparisons, with FDR<0.1 considered significant.

Due to the rarity of CNO, we will enroll as many patients as possible to increase the power of this study to observe difference responses among treatments.

A random percentage of subject visits will be selected throughout the course of the study for data quality checks. A second study team member will review the data for accuracy and address any errors that are identified.

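### NSAID responders and non-responders are defined by two different criteria that leave patients out, and the odds ratios for baseline ESR, CRP, imaging and clinical activity can partly reflect that definition

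*Protocol*

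**What the plan says.** The secondary endpoint in Protocol Section 8.0 is to "Determine the risk factors for patients with NSAID-refractory CNO". Two groups are formed.

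- **Responders:** "significant improvement of pain, focal exam, ESR, CRP, imaging within 6 months of NSAIDs treatment".
- **Non-responders:** "requiring >6 weeks of systemic glucocorticoid, disease modifying anti rheumatic drugs, TNF inhibitors, bisphosphonate".

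Both labels are assigned "based on treating physician's assessment". The analysis follows at once: "Baseline demographic, clinical, laboratory, imaging results will be compared between two groups and odds ratio will be calculated".

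The section gives no threshold for a significant improvement and does not say how the five domains combine. It also has no rule for a domain that was normal or unmeasured before NSAIDs, and no rule for a patient who meets both criteria or neither. Only the responder criterion carries a time limit for response. ESR and CRP are not named individually as candidate risk factors, but they fall under laboratory results.

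**The concern.** One group is defined by change in a set of measures and the other by a treatment decision. Baseline values of the same measures are then tested as predictors of group membership. Change depends on the starting value: a normal ESR has no room to improve, while a high one tends to fall through regression to the mean alone. Entry to the responder group can therefore depend on the baseline value being tested, while entry to the non-responder group does not depend on it in the same way. The same applies to pain and focal exam, because baseline clinical results are also compared. Demographic factors are not tied to the definition in this way.

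This is the protocol's only secondary endpoint, and it serves Aim 1 on clinical characteristics related to prognosis. An odds ratio for ESR, CRP or lesion activity that partly reflects the classification rule could be reported as a prognostic finding, or could mask a real one. The false discovery rate limit in Section 11.0 controls multiplicity, not this distortion. Covariate adjustment does not restore patients left out of a group.

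**Working it through.** The protocol gives no rate, odds ratio or sample size for this endpoint, so there is no figure to reproduce. The check has three parts.

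**1. Do the two criteria cover everyone once?**

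| Patient course on NSAIDs | Responder criterion | Non-responder criterion |
|---|---|---|
| Domains improve, no second-line treatment | met | not met |
| No improvement, second-line treatment needed | not met | met |
| Pain-free, markers normal throughout, no second-line treatment | unclear | not met |
| No clear improvement, no second-line treatment | not met | not met |
| Domains improve, second-line treatment still given | met | met |

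The last three rows have no unambiguous place. In the third, the answer turns on a baseline value.

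**2. Effect on a null odds ratio.** Suppose a raised baseline marker is unrelated to NSAID response.

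- Non-responders split raised:normal as a:b, and true responders split the same way.
- A share f of true responders with normal markers, and g of those with raised markers, is not counted.
- Counted responders then split a(1-g) : b(1-f).

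Odds ratio for non-response, raised versus normal = {a/[a(1-g)]} / {b/[b(1-f)]} = (1-f)/(1-g).

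The result does not depend on how common raised markers are. Neither f nor g is given in the protocol, so a range is shown.

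| f | g | Reported odds ratio (true value 1) |
|---|---|---|
| 0 | 0 | 1.00 |
| 25% | 0 | 0.75 |
| 50% | 25% | 0.50/0.75 = 0.67 |
| 50% | 0 | 0.50 |

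Losses unrelated to the marker raise f and g alike and cancel. If physicians also escalate more readily when markers are high, multiplying the odds of non-response by k, the reported value is k(1-f)/(1-g). This exceeds 1 once k > (1-g)/(1-f), for example 0.75/0.50 = 1.5 at f=50%, g=25%. The protocol gives no basis for k either.

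**3. Simulation with a continuous marker.** The inputs below are assumptions, not protocol figures.

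- 200,000 patients per scenario and a standardised marker.
- Baseline to follow-up correlation 0.3 to 0.9, with a mean fall of 0.5 SD.
- Improvement is a fall of at least 0.5 or 1.0 SD.
- Pain improves in 50%, independently of the marker.
- 40% are escalated, independently of the baseline marker, so the true odds ratio is 1.

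| Rule for the groups | Odds ratio per SD of baseline marker | Patients in neither group |
|---|---|---|
| Responder needs marker **and** pain improvement | 0.50 to 0.83 | 45% to 56% |
| Responder needs marker **or** pain improvement | 0.85 to 0.95 | 15% to 26% |
| Escalated versus not escalated | 0.99 to 1.01 | none |

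A hand check on the lower ends of the last column: at the 0.5 SD threshold half the patients improve on the marker, so the shares in neither group are 0.60 × (1 - 0.25) = 45% and 0.60 × 0.50 × 0.50 = 15%. These odds ratios are per SD and are not on the same scale as those in part 2. The last row is close to 1 because escalation was simulated as independent of the marker. It shows that the definition causes the shift in the rows above, not that escalation is free of marker influence in practice.

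**The case against.** The strongest reply is that the responder list is a bare comma list applied by a physician. Nothing says that all five domains must improve. The non-responder list has the same form and cannot sensibly require all four treatments. A physician may well call a pain-free patient with normal ESR and CRP a responder. Then f is near 0 and the distortion nearly vanishes. A combination rule could also sit in a statistical analysis plan that is not at hand. This stands as a limit on size. It does not remove the point, because the protocol itself fixes two different criteria, and the more lenient rule simulated still gave 0.85 to 0.95.

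Three stronger readings are tempting, and the protocol does not support them.

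- **Every normal-marker patient is excluded from the responders, so the odds ratio falls to 0.** This needs an all-five rule applied without judgement, which the protocol does not state. Using 1-f alone also ignores responders with raised markers whose values fall too little to count.
- **Raised ESR or CRP will look protective.** The responder rule alone acts in that direction. But non-response is defined by escalation, which high markers may prompt. Section 2.0 also notes consensus treatment plans for active spinal lesions, so baseline imaging may lead to escalation too.
- **Imaging before NSAIDs is often missing because MRI is optional.** The optional item in Section 3.0 concerns a window around enrollment, not NSAID start. Section 9.0 allows retrospective chart review of visits before consent.

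Testing baseline values as predictors of later response is not in itself an error.

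**Conclusion.** The point holds in a limited form. Section 8.0 uses two criteria that are neither mutually exclusive nor exhaustive, and one of them is built on change in measures whose baseline values are then tested. Odds ratios for baseline ESR, CRP, imaging and clinical activity can therefore be partly produced by the definition. Under assumed losses a null odds ratio moves to (1-f)/(1-g), from near 1 to 0.67 or 0.75 in the examples, with larger shifts under stricter rules. The size depends on f, g and a combination rule that the protocol does not state. The net direction cannot be settled from the protocol. Physician judgement may shrink the problem, but it may also let its extent differ between sites. The classification should be corrected before the next of the periodic analyses planned in Section 7.0.

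**What to change.** Amend the secondary endpoint in Section 8.0 as an analysis definition. Treatment decisions are unaffected.

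1. Use one mutually exclusive and exhaustive classification for the risk-factor analysis: for example, the existing non-responder criterion met versus not met within a fixed window after NSAID start. The investigators should set the window and say how patients with shorter follow-up are handled.
2. If the improvement list is kept, let a domain count only when it was measured and abnormal before NSAID start, and otherwise accept that it remains normal. Apply this to focal exam as well. Requiring focal-exam improvement of everyone would repeat the problem for patients with no focal finding at baseline. State how the domains combine and which label applies when both criteria are met.
3. Keep one primary response definition for all odds ratios so that they stay comparable. Add a sensitivity analysis that leaves out of the response definition any domain whose baseline value is being tested.
4. Report how many patients fall in neither group under the improvement list, by baseline marker status.

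An escalation-based classification removes the part due to the definition. It does not remove escalation prompted by the markers themselves, and this should be stated when results are interpreted.

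The cost is revised wording, a derived variable and a modest amount of extra analysis on data already collected. The small downside is that, in some patients, the responder label rests on fewer objective markers.

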1.0 Objectives

Objective

The objective of the study is to establish a prospective disease registry for chronic recurrent multifocal osteomyelitis (CRMO)/chronic nonbacterial osteomyelitis (CNO) in order to investigate the natural history of the disease and the responses of patients to different clinical managements over 5 years.

Aims

Aim 1: To determine the clinical characteristics that are related to prognosis

Aim 2: To compare the effectiveness of various clinical managements in practice setting.

Aim 3: To characterize the long-term outcome of CNO

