2.0 Background

Chronic nonbacterial osteomyelitis (CNO) is an autoinflammatory bone disease that mainly affects children and adolescents. Clinical presentations range from mild and sometimes limited unifocal disease to severe, chronically active or recurrent inflammation of multiple bones. The latter is referred to as chronic recurrent multifocal osteomyelitis (CRMO). Here we will use the term "CNO" to refer to the entire spectrum of this disease. CNO can be complicated by vertebral compression fractures, kyphosis, and leg length discrepancy when it is not recognized early or treated adequately. The diagnosis of CNO is made by excluding alternatives in the differential diagnosis including malignancy (leukemia, lymphoma, and primary or metastatic bone tumors), Langerhans cell histiocytosis, and infection. Clinical assessment in conjunction with serum inflammatory parameters and imaging studies, particularly magnetic resonance imaging (MRI), are crucial for the diagnosis and monitoring of disease activity of CNO¹.

Because of significant variation in clinical treatment practices among pediatric rheumatologists, standardized treatment regimens (consensus treatment plans, CTPs) have been developed within the Childhood Arthritis and Rheumatology Research Alliance (CARRA), a North American organization comprised of pediatric rheumatologists and researchers, for CNO patients with an NSAID-refractory course and/or with active spinal lesions². These CTPs provide an opportunity for pediatric rheumatologists to conduct comparative effectiveness research on CNO through prospective data collection. CRMO/CNO workgroup is comprised of pediatric rheumatologists from North America as well as international colleagues who are interested in collaborating in CNO research. Furthermore, risk factors of severe disease have been described by Wipff et al. based on a large retrospective cohort study³. Their results may be validated by an independent prospective cohort study. To date, there has been only one prospective study on CNO since its first description in 1972⁴. Therefore, we propose to establish this international registry of patients with CNO to accomplish above goals. Long-term

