7.0 Study Timelines

Study participation will commence when informed consent is signed and ends 20 years thereafter or sooner, if subject transitions to other practices.

We expect to approach all eligible subjects for participation therefore; recruitment and enrollment will be ongoing.

At this time, we plan to analyze the data periodically per the study aims above. Additional analyses may be added as IRB modifications in the future. Results of deidentified analyses may be shared with the clinical program team for quality improvement.

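### NSAID responders are defined by improvement within 6 months, non-responders by requiring another drug class with no stated NSAID exposure or time limit, so the groups can overlap, leave patients out and blur the secondary odds ratios

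*Protocol*

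**What the plan says.** Protocol Section 8.0 sets a secondary endpoint of risk factors for NSAID-refractory CNO and splits patients into two groups. The first is "NSAID responders (significant improvement of pain, focal exam, ESR, CRP, imaging within 6 months of NSAIDs treatment"). The second is "NSAID non-responders (requiring >6 weeks of systemic glucocorticoid, disease modifying anti rheumatic drugs, TNF inhibitors, bisphosphonate) based on treating physician's assessment". The analysis follows directly: "Baseline demographic, clinical, laboratory, imaging results will be compared between two groups and odds ratio will be calculated".

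Four other places bear on how these definitions work:

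- Section 7.0: participation "ends 20 years thereafter or sooner, if subject transitions to other practices", and "we plan to analyze the data periodically per the study aims above".
- Section 1.0: the objective covers "the responses of patients to different clinical managements over 5 years".
- Section 2.0: the consensus treatment plans were developed "for CNO patients with an NSAID-refractory course and/or with active spinal lesions".
- Section 3.0: the inclusion list covers MRI, whole-body imaging and biopsy. It asks for no NSAID trial.

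Section 13.0 leaves treatment decisions entirely to the treating physician.

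**The concern.** The two groups are not complements on one scale. One is defined by an outcome (improvement on NSAIDs) with a time limit. The other is defined by a treatment event (requiring another drug class) with none. The six-week figure in the second definition belongs to the other treatment, not to NSAIDs.

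An odds ratio for NSAID-refractory disease needs a denominator of patients who could have responded to an NSAID and one point at which response is judged. Without these, a baseline feature that influences drug choice or later escalation can be associated with the non-responder label even if it has no bearing on NSAID response. Spinal involvement is an example. An association that is real can also be diluted. The list of risk factors, which is the purpose of this endpoint, would be read as being about NSAID failure when it is partly about something else.

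**Working it through.** **Step 1: apply the two definitions to four kinds of patient.**

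| Patient | Responder text | Non-responder text |
|---|---|---|
| Improves by month 6, never requires a listed drug | met | not met |
| Improves by month 6, requires a listed drug in year 3 | met | met |
| Given a listed drug with no NSAID trial | not met | can be met |
| No significant improvement, no listed drug required | not met | not met |

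Only the first row is settled. No section gives a precedence rule for the second, an exposure condition for the third or a place for the fourth.

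**Step 2: possible size.** The protocol gives no figure to reproduce. Every input below is an assumption.

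*Direct starts.* Let p be the proportion who would not respond to NSAIDs, f the share started directly on another class and h the share of direct starters who would have failed NSAIDs (h = p if unrelated). Then NR = p − f·h and R = (1 − p) − f·(1 − h). If direct starters count as non-responders, the odds are (f + NR)/R; if they are excluded, NR/R. Subscript 1 is with the feature, 0 without.

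True odds ratio 1.0, h = p, direct starters counted:

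- p = 0.5, f1 = 0.25, f0 = 0: (0.25 + 0.375)/0.375 = 1.667, against 0.5/0.5 = 1, gives **1.67**.
- p = 0.5, f1 = 0.25, f0 = 0.10: 1.667/1.222 = **1.36**.
- p = 0.5, f1 = 0.10, f0 = 0.05: 1.222/1.105 = **1.11**.
- f1 = 0.25, f0 = 0: **2.11** at p = 0.3 and **1.48** at p = 0.7.
- f1 = f0: **1.0**.
- Extreme case, f1 = 0.50, f0 = 0: 3.00 at p = 0.5 and 4.33 at p = 0.3.

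*Overlap.* If month-6 responders who later require a listed drug at a constant annual rate are relabelled, the relabelled share is r = 1 − exp(−rate × T), and the odds are [p + (1 − p)r]/[(1 − p)(1 − r)]. With p = 0.5 in both groups (month-6 odds ratio 1.0):

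- 4% versus 2% a year: at 5 years r = 0.181 and 0.095, odds ratio **1.19**; at 20 years r = 0.551 and 0.330, odds ratio **1.74**.
- 3% versus 2% a year: **1.09** and **1.33**.
- Equal rates: **1.0** at both times.

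*Bias the other way.* Take a true odds ratio of 2.0 with p0 = 0.40 and p1 = 0.571. If the same share r of responders in both groups is relabelled, r = 0.1, 0.2 and 0.4 give **1.87**, **1.77** and **1.62**. At r = 0.4, for example, the labelled proportions are 0.743 and 0.640, with odds 2.889 and 1.778. So neither the size nor the sign of the bias is fixed.

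**Step 3: does excluding direct starters cure it?** True odds ratio 2.0 (p1 = 0.667, p0 = 0.5), f1 = 0.25, f0 = 0:

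| h1 | Direct starters excluded | Direct starters counted |
|---|---|---|
| 0.667 (unrelated) | 2.0 | 3.0 |
| 1.0 (all would have failed) | 1.25 | 2.0 |
| 0.333 | 3.5 | 5.0 |

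Exclusion is right only if direct starting is unrelated to latent response within levels of the feature. The last row shows that the two results need not bracket the truth.

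**The case against.** The group is called NSAID non-responders, the word requiring implies need, and the classification rests on the treating physician. A sensible physician need not give that label to someone who never took an NSAID. This stands as a limit on the direct-start problem. It is not a written rule, though, and physicians at many international sites may apply it differently. It also does not settle the overlap: early improvement and later need can both be recorded truthfully for one patient.

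A reader might infer three stronger things that the protocol does not support:

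- *That only non-responders are classified subjectively.* The reference to the physician's assessment ends the sentence that defines both groups and can be read as governing both.
- *That patients with spinal lesions skip NSAIDs.* Section 2.0 gives the population of the treatment plans. It does not say which drugs they contain or that NSAIDs are bypassed. It permits direct starts but does not establish them.
- *That labels are revised at each periodic analysis.* No section says so. Twenty years is a ceiling, and Section 1.0 speaks of 5 years. The 1.74 above needs full 20-year follow-up, constant unequal rates and relabelling together.

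It is also fair to say that visit windows belong in a statistical analysis plan, which is not shown here and may exist. But the protocol itself writes the group definitions and ties the odds ratios to them, and a plan that applied them as written would inherit the fault.

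**Conclusion.** The point holds as a fault of definition. Section 8.0 puts the two groups on different axes, with no NSAID exposure or time limit for non-responders, no rule when both definitions are met and no group for patients who meet neither. The secondary odds ratios can therefore partly reflect drug choice or length of follow-up rather than NSAID response.

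How often this would happen, and how far and in which direction the odds ratios would move, cannot be derived from the protocol. The worked values show only what is possible under assumed inputs, including no bias at all. It would be wrong to conclude that the results will be inflated. The primary endpoint, based on the CDAS, does not use this classification and is not affected. Severity is minor to moderate.

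**What to change.** Reword the secondary endpoint in Section 8.0. This is a rule for analysis and sets no rule for treatment.

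- (a) Base the main odds-ratio comparison on patients with a recorded NSAID exposure, and state what counts as recorded.
- (b) Judge both groups once, on the same 6-month horizon from NSAID start, by the treating physician on the domains already listed.
- (c) Count as non-responders those without significant improvement by then, and those who by then required a listed drug as already worded (keeping the >6 weeks qualifier) because of inadequate NSAID response. State openly that this assigns patients who neither improve nor escalate, whom the present text places in neither group.
- (d) Later need for a listed drug does not change the label and is reported separately.
- (e) Report patients started on a listed drug without NSAID exposure, or for another recorded reason, as a separate category. Add a sensitivity analysis that counts them as non-responders. State the assumption behind the restriction and that the two results need not bracket the truth.

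Visit-window details can go in the statistical analysis plan.

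**Cost.** A reworded definition, one extra analysis and possibly one case report form field for the reason a drug was started. The chart review and medication questions in Section 9.0 already supply most of the rest, though dates and reasons before enrolment may be incomplete.

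Fewer patients are compared. If 25% of spinal and 10% of other patients start directly (assumed), the share leaving is s × 0.25 + (1 − s) × 0.10 for spinal share s:

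- s = 0.2: 5.0% + 8.0% = 13.0% of the cohort, of whom 38% are spinal.
- s = 0.3: 7.5% + 7.0% = 14.5%, of whom 52% are spinal.
- s = 0.4: 10.0% + 6.0% = 16.0%, of whom 62.5% are spinal.

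With the 3 to 12 month visit spacing in Section 9.0, some patients will not be assessable at the horizon and should be reported as such. Restriction can itself bias the odds ratio if direct starts are related to latent NSAID response, and differences between physicians in when they escalate remain.
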